1.0 Study Summary

Study Title	A quasi-experimental, interrupted time series study to evaluate the effectiveness of “SexHealth Mobile” on uptake of contraception in women with substance use disorder
Study Design	A quasi-experimental study design using an interrupted time series (i.e., usual care [control] then intervention care) to compare uptake of contraception before and after implementing the “SexHealth Mobile” intervention.
Primary Objective	To improve access to highly effective contraception among women with substance use disorder (SUD) with our pilot program “SexHealth Mobile”.
Secondary Objective(s)	To explore intervention feasibility
Research Intervention(s)/ Investigational Agent(s)	Our study intervention consists of “SexHealth Mobile” which integrates two existing services in our community: a mobile medical unit (MMU) operated by Swope Health Services, and “SexHealth” a point-of-care contraception counseling service that our research team developed for Children’s Mercy Hospital’s emergency department (ED).
IND/IDE #	N/A
Study Population	Study population includes women with substance abuse disorder (SUD) with an unmet need for contraception who are accessing health, recovery, or community services recovery sites committed to our community partner, Swope Health Services. We will also enroll staff and clinicians from Swope Health who will perform tasks (including contraceptive counseling) relevant to health care delivery in the mobile medical unit.
Sample Size	Total sample size is: Women with SUD = 160 (We need 160 with evaluable data at end of index visit with 80 in each time period so will request to enroll up to 170 if needed) – Usual Care [control]: up to 85 – SexHealth Mobile intervention: up to 85 Staff/Clinicians from Swope Health Services = 10
Study Duration for Individual Participants	Women with SUD = Total study duration will be 3 months for all participants. Follow-ups will be conducted at 2-weeks, 1-month, and 3-month post-enrollment. Staff/Clinicians from Swope Health Services = 18 months
Study Specific Abbreviations/ Definitions	SUD: substance abuse disorder OUD: opioid use disorder MMU: Swope’s medical mobile unit ED: emergency department

Objectives and Hypotheses

1.1 Our primary objective is to improve access to highly effective contraception among women with substance use disorder (SUD) with our pilot program “SexHealth Mobile”.

– **Our primary hypothesis** is that current use of highly effective contraception (includes *sterilization, subdermal implant, intrauterine device, injectable, pill, patch, or ring*) will be greater at 1-month post-enrollment among women recruited during the intervention period (i.e., “SexHealth Mobile”) compared to those recruited during the usual care period. We will also compare current use and discontinuation rates at 2-weeks and 3-months among all participants.

1.2 Our secondary objective is to explore intervention feasibility.

2.0 Background

2.1 Scientific Background and Prior Experiences

Women with SUD experience higher rates of pregnancy complications including miscarriage, placental previa/abruption, and stillbirth. Substance-exposed infants, including those with neonatal abstinence syndrome (NAS) and fetal alcohol spectrum disorders (FASD), are more likely than non-exposed infants to be born preterm, have low birth weight, and require intensive care hospitalization [1]. SUD in pregnancy is common; about one in four pregnant women report substance use (including tobacco) [1]. And the national prevalence of women presenting in pregnancy specifically with opioid use disorder (OUD) increased by 333% from 1999 to 2014 [2].

Most pregnancies among women with SUD are unintended [3], often due to contraception non-use or misuse resulting from a confluence of patient- provider- and system-level barriers. In particular, OUD is growing problem among pregnant women in the U.S. Midwest, as rates of neonatal abstinence syndrome have grown by 270 percent in the state of Missouri over the past decade [2]. Meta-analyses have estimated the prevalence of contraceptive use among women with SUD at only 55% [4], highlighting the urgent need for effective patient-centered interventions that increase access to contraception for women with SUD by integrating contraceptive counseling into existing recovery resources or other points of contact.

Many women with SUD never learn about contraceptive options as they often avoid seeking routine health care. Limited data suggests that when women with SUD use contraception, they most commonly use methods with lower rates of efficacy (i.e., oral contraceptive pills and condoms) and often make errors, rendering these methods even less effective than usual [4]. Identifying novel points of contact where women with SUD may be receptive to learning about and/or obtaining the most effective methods is key to reducing opioid-exposed pregnancies.

2.2 Formative Research and Preliminary Data

We conducted in-depth interviews with women who abused substances (e.g., opioids, alcohol, methamphetamines) throughout Missouri. Though many wanted to avoid pregnancy, women reported infrequent use of effective contraception. Due to their current financial/health/relationship instability, most were very receptive to receiving contraceptive care, including long-acting reversible contraception (LARC), in non-traditional settings such as mobile medical units and treatment or recovery centers. We also interviewed professionals who provide care or treatment for this population (e.g., treatment center managers, physicians). Providers agreed that access to contraception could be an important harm reduction strategy but identified barriers that interfere with delivery of this care. Most clinics and recovery centers do not actively identify unmet reproductive needs among this high-risk population. Further, many prescribing clinicians had limited experience in providing contraception directly, preferring to refer women to traditional clinic settings for this care.

Previously, our team developed and pilot-tested an intervention (SexHealth) to bring point-of-care sexual risk reduction counseling and sexual health services (e.g., contraception, condoms) to adolescents visiting the emergency department. In a randomized controlled trial (N=81), the intervention was acceptable to 95% of adolescents and feasible (mean length of session was 24.5 minutes). Compared to controls, intervention participants were more likely to complete ≥1 service (69% vs. 90%, p=0.028).

3.0 Study Endpoints

- 3.1 Primary Endpoint: Study will end data collection when the estimated sample size has been enrolled to show statistically significant effects for women with any type of SUD, including those with OUD.

4.0 Study Intervention and Drug Handling

4.1 Description:

Our study intervention consists of “SexHealth Mobile” which integrates two existing services in our community: a mobile medical unit (MMU) operated by Swope Health Services, and “SexHealth” a point-of-care contraception counseling service that our research team previously developed for Children’s Mercy Hospital’s

emergency department (ED). Using a menu of adaptive services, "SexHealth Mobile" will bring contraceptive care to women with SUD (including a subset of women with OUD), if they wish to receive it, at targeted recovery sites Swope currently partners with.

- 4.2 Drug Handling: All drugs and devices being dispensed are standard of care treatments. Swope Health will have sole responsibility of all study medications which includes storage, handling, and dispensing of drugs and devices (i.e., subdermal implants). Upon receipt by the designated person at Swope ([name], DNP), devices and medications would be logged and accounted for then appropriately stored in secured location. Devices and medications would be labeled for the individual patient upon receipt of clinician order. The Swope staff members will responsible for filling individual patient containers and labeling the containers following their established procedures. The Swope staff will be responsible for keeping accurate records of the clinical supplies, the amount dispensed to and returned by the patients, and the disposition at the end of the study.
- 4.3 The contraceptive medications and/or subdermal implant that may be used in this study are not investigational as this study does not aim to evaluate the safety or effectiveness of these therapies.

5.0 Procedures Involved

5.1 Study Design:

A quasi-experimental study with an interrupted time series (i.e., usual care [control] then intervention care) to compare the uptake of contraception before and after implementing the "SexHealth Mobile" intervention. Participants recruited will be women with SUD/OUD with an unmet need for contraception who are accessing health, recovery, or community services at centers where Swope Health already provides clinical care (but not contraception). The recovery centers include: Healing House, ReDiscover, Journey to a New Life, and Amethyst Place. We are partnering with Swope Health Services to integrate the "SexHealth Mobile" model into their existing MMU that currently provides limited clinical services.

5.2 Research Procedures:

Usual care: Study staff will work with a point person at each of the recovery sites to facilitate recruitment logistics according to the site's COVID- related restrictions. Recruitment will continue until the target sample size has been reached (up to 6 months). Staff will work with recovery sites to reach and identify women that may be interested and meet eligibility criteria.

Study staff will distribute recruitment information virtually to the sites in the form of electronic recruitment document. We will also create a video with recruitment information for the sites to distribute.

SHORT TITLE: SexHealth Mobile

Interested participants may be given options to meet in-person or call-in information for a TEAMS meetings that will serve as recruitment sessions. Women will speak to a member of the study staff, complete eligibility, informed consent, and the baseline survey. In-person recruitment may also occur. In this case, we will use our approved COVID-19 contingency plan to minimize risk of COVID transmission, including using outdoor spaces, wearing masks, maintaining social distance, and sanitizing all materials. We will also adhere to participating sites COVID-19 safety guidelines during this time.

During recruitment, women will complete an eligibility screen, informed consent, and baseline survey via REDCap surveys. All participants will be assigned a unique patient identifying number through REDCap.

If a participant is eligible and has agreed to consent, she will complete the baseline survey and provide contact information for the designated follow-up surveys and reminders that will be completed at 2-weeks, 1-month, and, 3-months after baseline. Study staff will then provide information about contraceptive services according to referral procedures followed at the specific recovery site where recruitment is taking place. The usual care referral document will be reviewed and sent to the participant electronically via TEAMS or email, and hard copies will also be mailed or dropped off to each participant at the site along with their Greenphire payment card.

If participant is not eligible, study staff will provide a referral on where they can access more information on contraception and care.

Follow-up survey reminders will be sent via email and text messages for participants to call study staff. Text message reminders will be sent via Twilio on REDCap.

Intervention (“SexHealth Mobile”): After usual care sample has been reached, Swope Health will begin integrating “SexHealth Mobile” into their health care services for women. These services include the MMU with in-person visits with a Swope health care provider. Study staff will work with recovery sites to disseminate information about the “SexHealth Mobile” and build interest in the intervention. This will be focused on raising awareness about the clinical service, not direct recruitment for the research study. Recovery site leaders will be instructed to direct any questions pertaining to the research study to the study team.

At the start of the “SexHealth Mobile” intervention, study staff will continue to recruit women virtually or in-person with the sites to participate in surveys about their experience and the care provided. If permitted, we will use similar procedures to conduct in-person recruitment using our approved COVID-19 contingency plan. At the end of the baseline survey, women who are interested in obtaining services with SexHealth mobile will be given an appointment for

SHORT TITLE: SexHealth Mobile

virtual counseling and/or mobile health on-site services (depending on Swope's clinical care procedures at the time).

We estimate the research team will need 4-6 months in order to recruit the target sample of "SexHealth Mobile" patients.

Participants will complete an eligibility screen and informed consent with study staff via TEAMS or in-person. If a participant is eligible and has agreed to consent, she will complete the baseline survey on an iPad via REDCap. All participants will be assigned a unique patient identifying number through REDCap. Participants will also provide secure contact information for the designated follow-up surveys and reminders that will be completed at 2-weeks, 1-month, and, 3-months after baseline.

After completing the baseline, study staff will ask participants if she would like to be seen for contraceptive counseling. Women who are interested in obtaining services with SexHealth mobile will be given an opportunity to acquire an appointment for virtual or in-person counseling on the MMU or on-site services (depending on Swope's clinical care procedures at the time).

Swope providers will be given an audio recorder to record visits with participants to assess for intervention fidelity. If participant wishes to not be recorded, they will be given the option to turn off the recorded at any time during their visit.

After the visit is completed, participants will complete a brief post-intervention survey over the phone or in-person with study staff and be provided a referral to follow-up.

If participant does not want to be seen or acquire an appointment with a healthcare provider after baseline, study staff will provide a referral virtually or in-person on where they can access more information on contraception and care.

If participant is not eligible, study staff will provide a referral virtually or in-person on where they can access more information on contraception and care.

Follow-up survey reminders will be sent via email and text messages for enrolled participants to call study staff. Text message reminders will be sent via REDCap through Twilio or other CM approved messaging.

5.3 **Procedures for lessen risk:**

Data and safety will be monitored on multiple levels. Drs. [name] and [name], the lead Research Coordinator and research staff will meet at least weekly to review study progress, safety issues, recruitment progress, and data quality. The entire research team will meet quarterly to review study progress. The Research Coordinator will produce quarterly reports describing recruitment milestones, adverse events, and data quality. We will report any adverse events as directed by the institutional IRB and adverse event (AE) reporting policies. Events will be reported promptly to the PIs and the lead Research Coordinator who will make provisions to

respond appropriately, ensuring referral to medical/professional resources, as needed. All data collected will be stored and secured on REDCap on password protected computers. Access will only be granted to study staff. Contact information will be marked as “identifiers” in the secure REDCap project, stored on a REDCap instrument separate from the other study data, and not downloaded along with the dataset for analysis.

In addition, participants interested in birth control will be given verbal and printed evidence-based information about the method (these information sheets are publicly available at reproductiveaccess.org). This includes information about possible side effects and risks associated with the medication.

For participants who start a medication, we will ask about common (expected) adverse events at each follow-up survey. The vast majority of medication side effects are mild and often don't require any intervention or care. Participants will be given guidance (anticipatory) for side effect management at enrollment and also if side effects are disclosed during survey follow-up. Participants will be instructed to contact Swope Health for mild side effects and this number will be provided to participants (written and verbally). For more concerning side effects, (i.e., chest pain, trouble breathing, weakness or numbness on part of the body, bad headache, or leg swelling/redness/pain), participants will be directed to seek care at the nearest emergency department or to call 911.

5.4 Data collection:

Our multi-disciplinary team developed the assessment tools, based on national surveys and a review of the pertinent literature including validated items where applicable. At baseline, we will assess for high-risk sexual behaviors, substance use, relationship status, health care access and utilization, health history (e.g., pregnancies, mental health), and demographic information. Follow-up surveys will assess for contraception use (including condoms), healthcare utilization, health history, intervention satisfaction and feasibility.

Baseline information will be collected directly from participants on an iPad recorded on REDCap. Follow-up surveys will be completed after enrollment and recorded in REDCap.

See our measure tools to know what demographic, baseline, and follow-up data will be collected.

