11.0 Local Number of Subjects

11.1 We anticipate enrolling up to 170 new participants to reach out target sample size of 160 with evaluable data (up to 85 during the usual care period, and up to 85 during the intervention period). This is in addition to the 31 recruited in the first attempt to be in the study before COVID-19, meaning a total of 201 women will be enrolled in the study. Additionally, we will recruit up to 10 Staff/Clinicians from Swope Health Services.

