12.0 Screening and Recruitment Methods

12.1 For the usual period, recruitment will occur through recovery sites at certain weekly rotations throughout the 6-month period. Participants will be presented with a recruitment flyer (virtually or in person) and ask if they are interested in participating by study staff. We will have a peer outreach coordinator at each site to help elicit participation interest. If a participant is interested, study staff will screen the participant for eligibility on REDCap via a tablet, their personal mobile device, or a computer available at their site.

12.2 During the intervention period, study staff will recruit at the recovery sites based on the mobile clinic's stop schedule. If MMU is not available, study staff will recruit based on certain weekly rotations that are provided by Swope's health care provider. Participants will be presented with a recruitment flyer (virtually or in person) and ask if they are interested in participating by study staff. We will have a peer outreach coordinator at each site to help elicit participation interest. If a participant is interested, study staff will screen the participant for eligibility via a tablet on REDCap.

12.3 All identifying information will be collected after participant has been screened and consented

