23.0 Setting

- 23.1 Research procedures will be conducted at recovery centers Swope Health Services currently partner with. These centers include Healing House, Hope City, ReDiscover, and Amethyst place for both the usual care and intervention period. Contraceptive counseling will be conducted on the MMU. Study staff will ensure all settings have private rooms for participants to complete procedures. Permission to conduct research procedures at these centers will be sought out.

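### The two center lists disagree, and neither recruitment nor analysis keeps the center mix constant between usual care and intervention, so period can be confounded with center.

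*Combined protocol and SAP*

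**What the plan says.** All references are to the combined protocol and SAP.

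- **Centers.** Section 5.1: "The recovery centers include: Healing House, ReDiscover, Journey to a New Life, and Amethyst Place". Section 23.1: "These centers include Healing House, Hope City, ReDiscover, and Amethyst place for both the usual care and intervention period".
- **Targets.** Section 11.1 sets enrolment as "up to 85 during the usual care period, and up to 85 during the intervention period". Section 5.2 lets usual care recruitment run until its overall target is met. No section gives a target, cap or matching rule by center.
- **How women are reached.** Usual care, section 12.1: "recruitment will occur through recovery sites at certain weekly rotations throughout the 6-month period". Intervention, section 12.2: "study staff will recruit at the recovery sites based on the mobile" clinic's stop schedule, or on rotations supplied by the health care provider when the unit is not available.
- **Comparator.** Under section 5.2, usual care information is given "according to referral procedures followed at the specific recovery site where recruitment is taking place".
- **Analysis.** Section 18.1 compares use of highly effective contraception at 1 month with Fisher's exact test. It adds logistic regression on potential predictors, without listing them. Center is not mentioned.

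**The concern.** This is a non-randomized before/after comparison. Holding the sites constant is one of the few protections such a design has against confounding. Here the set of sites is stated in two ways, and nothing fixes the share of women that each site supplies in each period. The rule that decides which sites supply women changes when the intervention starts, so the mix can shift systematically and not only by chance.

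Center is plausibly related to outcome. Clients may differ between centers, and the control condition itself follows each site's referral practice. If the mix shifts, part of the period difference reflects who was recruited and what usual care meant where they were recruited. The planned test has no means of separating that from the effect of SexHealth Mobile.

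**Working it through.** **1. The lists side by side**

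| Center | Section 5.1 | Section 23.1 |
|---|---|---|
| Healing House | yes | yes |
| ReDiscover | yes | yes |
| Amethyst Place | yes | yes |
| Journey to a New Life | yes | no |
| Hope City | no | yes |

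Three centers are common, and each list has one that the other lacks. Section 23.1 ties its list to both periods; section 5.1 ties its list to neither.

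**2. The plan's own sample size (section 18.3)**

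The inputs are 20% v 76%, 90% power and alpha 0.05, with a stated total of 32. Exact Fisher power with equal groups is 92.6% one-sided at 16 per period (89.7% at 15), which reproduces 32. The two-sided power at 16 is 85.4%. Then 32/0.30 = 106.7, stated as 107, and 107 x 1.5 = 160.5, stated as 160. Center enters nowhere, so this point changes none of these figures. They give the two sizes used below: about 53 per period after attrition (107/2 = 53.5) and 80 with none.

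**3. How center mix enters the crude difference**

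If the intervention does nothing, the expected period difference is the sum over centers of (share in intervention - share in usual care) x center uptake. It is zero only if the shares match or uptake does not vary by center. The plan secures neither.

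**4. Illustration under assumptions**

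The documents give no uptake or enrolment share by center, so every center rate and share here is assumed. The test is two-sided Fisher at 0.05, with no intervention effect, treating each woman as an independent draw from her period's pooled rate.

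Example, same centers in both periods, with the high-uptake centers' share moving from 20% to 60% and uptake 10% v 40%:
- usual care: 0.8 x 10% + 0.2 x 40% = 16%
- intervention: 0.4 x 10% + 0.6 x 40% = 28%
- spurious difference: 12 points

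| Assumed scenario | Pooled uptake | Spurious difference | Rejection, 53 per period | Rejection, 80 per period |
|---|---|---|---|---|
| Same mix, 20% everywhere | 20% v 20% | 0 | 3.0% | 3.2% |
| Same centers, high-uptake share 20% to 60%; 10% v 40% | 16% v 28% | 12 points | 24.9% | 38.4% |
| Same centers, same shift; 20% v 60% | 28% v 44% | 16 points | 33.9% | 50.0% |
| One-period centers, 25% share; 20% v 40% | 20% v 25% | 5 points | 6.3% | 8.6% |
| One-period centers, 25% share; 20% v 60% | 20% v 30% | 10 points | 16.3% | 25.0% |

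The second and third rows need no change of centers, only an unbalanced mix. The last two show what would follow if a center took part in one period only, which the documents do not plan. The signs are arbitrary: a shift the other way would hide a real effect.

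**5. What adjustment can do**

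In the second and third rows the within-center difference is zero, so stratifying by center removes the bias. In the last two rows the one-period centers have no counterpart. A Cochran-Mantel-Haenszel analysis gives such centers no weight, whereas the crude test counts them in full.

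**The case against.** Several points on the other side stand.

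- **No switch is planned.** A reader might infer that one center will serve usual care and another the intervention. The text does not support this. Section 23.1 applies its list to both periods, so using a different list in each would breach it. Both lists are also introduced by the word include; five centers open in both periods would satisfy both sentences. The discrepancy may be an update made in only one section.
- **The bias cannot be sized from the documents.** A reader might take the 66% and 85% in section 18.3, apply them to one center in four, and obtain 0.25 x 19 = 4.75 points. That does not hold. Those figures come from outside studies of point-of-care contraception and contrast active drug users with women in recovery, not centers. The calculation also needs four equal centers and a complete swap.
- **The planned effect is large.** The shifts illustrated are well below 56 points (76% - 20%). If the true effect were that large, they would alter the estimate but hardly the conclusion. They matter more if the true effect is smaller.
- **Usual care may be partly common across sites.** Section 5.2 also mentions a usual care referral document. How far referral differs by site is not stated.
- **The planned logistic regression could include center.** It could, but center is not pre-specified, so the plan as written does not protect the comparison.

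What remains is that the lists conflict, nothing holds the mix constant, the recruitment mechanism differs by period, and the analysis ignores center.

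**Conclusion.** The point holds as a risk of confounding that following the plan as written leaves open. The conflict between sections 5.1 and 23.1 is certain. The absence of any control of center mix, in enrolment or in analysis, is also certain from the current text. Whether the mix will differ, in which direction and by how much cannot be known from the documents.

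The stronger basis is the change of recruitment mechanism between sections 12.1 and 12.2 combined with period-only targets; the list conflict on its own does not show that centers will change. The 12 to 16 points and the 25% to 50% false-positive rates rest wholly on assumed center rates and shares. They show that the mechanism can matter at this sample size; they do not estimate the bias.

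**What to change.** 1. Reconcile sections 5.1 and 23.1 to one list, stated to apply to both periods.
2. In section 18.1, base the primary 1-month comparison on centers that enrolled women in both periods, stratified by or adjusted for center: Cochran-Mantel-Haenszel, or the logistic regression already planned, with period and center as terms.
3. Keep the unadjusted all-center Fisher comparison as a sensitivity analysis.
4. Report enrolment by center and period.

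Per-center enrolment quotas are not required. Recruitment follows the mobile unit's stops, and section 24.3 puts attendance at 2 to 14 clients per session, so quotas would be hard to meet. Adjustment deals with imbalance among shared centers more simply.

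The cost is protocol wording and a tally. A few women leave the primary comparison if a center recruits in only one period. As an assumed bad case, losing one of four equal centers in each period takes 53 to about 40 per period (0.75 x 53). That remains ample for 20% v 76%, since two-sided Fisher power is already 92.6% at 20 per period. The opioid use disorder subgroup is tighter: after the planned attrition, 16 per period would fall to about 12 (0.75 x 16), below the number on which section 18.3 rests. That is a further reason to settle the list before enrolment and keep every center open in both periods.

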9.3 Exclusion Criteria for subjects

Participants will be ineligible if they:

- have previously enrolled in the study
- are unable to provide informed consent
- are pregnant at index (recruitment) visit

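### SexHealth Mobile may open at the shared sites once usual-care enrolment, not follow-up, is complete, so control women could use it before their 3-month survey and dilute that comparison

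*Combined protocol and SAP*

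**What the plan says.** - **Start of the intervention (5.2).** The trigger is the usual-care sample: "After usual care sample has been reached, Swope Health will begin integrating" SexHealth Mobile into its care for women. Study staff also work with the sites to make the service known: "This will be focused on raising awareness about the clinical service, not direct recruitment for the research study".
- **How the sample is counted.** Section 1.0: "We need 160 with evaluable data at end of index visit with 80 in each time period". Section 5.2 ends usual-care recruitment when the target is reached, within 6 months at most.
- **Sites.** Section 23.1 uses its listed centers in both periods. The lists in 5.1 and 23.1 differ by one center; three are common to both. According to 5.1, Swope Health gave clinical care but no contraception at these centers beforehand.
- **Limits on control women.** Section 9.3 excludes women who "have previously enrolled in the study". That concerns the study, not the clinical service.
- **Usual care (5.2).** Control women receive a referral document for contraceptive services.
- **Comparisons.** The primary hypothesis is set at 1 month. Section 1.1 adds: "We will also compare current use and discontinuation rates at 2-weeks and 3-months among all participants". Section 18.1 plans the 2-week and 3-month comparisons of use, and also a summary and comparison of follow-up survey data, which under 5.4 include healthcare utilization.
- **Calendar (8.1).** Eighteen months in total: 3 of preparation, about 6 of recruitment in each period, and 2 of analysis. A chart follows whose columns are uncertain in the extracted text.

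**The concern.** What opens is a clinical service with site-wide publicity, not an arm closed to non-participants. Control women entered with an unmet need for contraception (9.2), so those still at the centers belong to the group the publicity addresses. If some obtain contraception through SexHealth Mobile before their 3-month survey, they are still analyzed as usual care. The control rate then rises for a reason that belongs to the intervention, and the 3-month difference is understated. Because the chance of exposure grows with time since enrolment, the difference could shrink between 1 and 3 months even if nothing changed among intervention women. The 3-month survey is the plan's only evidence beyond 1 month, and section 18.1 has no rule for identifying or handling control women who used the service.

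**Working it through.** **Inputs**
- Usual-care recruitment R: 6 months (5.2, 8.1), or 4 months if the section 8 chart is read by its apparent columns (usual-care recruitment from month 4, follow-up from month 8, intervention recruitment from month 9).
- Gap g from the end of control recruitment to launch: the prose gives none, so 0 is an assumption; the apparent chart layout gives 1 month.
- Rates: 20% and 76% (18.3). These are planning assumptions about uptake, borrowed here for use at 3 months.
- Analyzed size: 107 women after attrition (18.3), split 53/54.
- Share u of exposed controls who use the service: not in the documents; 10%, 25% and 50% are assumed.
- Accrual: assumed uniform, then varied.

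**The plan's own figures.** 76 − 20 = 56 points. 32/0.30 = 106.7, rounded to 107; 107 × 1.5 = 160.5, stated as 160. They serve only as inputs here. The plan gives no figure for control exposure.

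**Step 1: does the calendar leave room for control follow-up to finish first?** 18 − 3 (preparation) − 2 (analysis) − 3 (last follow-up) = 10 months for both recruitment periods. Six plus 4 fits with no gap; 6 + 6 does not fit. Waiting 3 months for control follow-up would need 3 + 6 + 3 + 4 + 3 + 2 = 21 months, or 23 with 6 months of intervention recruitment. The stated durations do not reserve that time.

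**Step 2: share of controls surveyed after launch.** Under uniform accrual, f = (3 − g)/R.

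| | g = 0 | g = 1 | g = 2 |
|---|---|---|---|
| R = 6 | 50% | 33% | 17% |
| R = 4 | 75% | 50% | 25% |

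The prose with an assumed zero gap and the apparent chart layout both give 50%. With linearly front- or back-loaded accrual, those two cases give 25% or 75%.

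**Step 3: effect on the 3-month comparison.** Suppose users reach 76%. Control rate = 0.20 + f × u × 0.56. At f = 0.50:

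| u | Control rate | Difference from 76% |
|---|---|---|
| 0 | 20% | 56 points |
| 10% | 22.8% | 53 points |
| 25% | 27% | 49 points |
| 50% | 34% | 42 points |

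The extremes are 0.167 × 0.10 × 0.56 = 0.009 (1 point lost) and 0.75 × 0.50 × 0.56 = 0.21 (21 points lost).

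**Step 4: the 1-month primary test.** Exposure is (1 − g)/R: 0 on the chart, 1/6 = 17% with R = 6 and no gap. In the latter case the control rate is 22.3% at u = 25% and 24.7% at u = 50%. Two-sided exact Fisher power against 76% with 53/54 women is above 99.9% at both.

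**Step 5: what the planned analyses would show.** At f = 0.50 and u = 25%, the chart schedule takes the difference from 56 points at 1 month to 49 at 3 months; the no-gap schedule takes it from 54 to 49. In this model the intervention group stays at 76% and the control group rises. A true decline would instead lower the intervention percentage and appear as discontinuation. The planned comparisons distinguish those two patterns. They do not distinguish a control rise caused by SexHealth Mobile from one caused by late action on the usual-care referral.

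**The case against.** **Actual use may be low.** In 5.2 only intervention women are approached after baseline: "study staff will ask participants if she would like to be seen for contraceptive counseling" is a step in the intervention period. Section 18.3 calls the population highly transient, so some controls will have left the sites. The share f also counts a woman whose survey falls days after launch. With uniform accrual, exposed controls would have had access for 1.5 months on average with R = 6 and no gap, and 1 month on the chart. This stands: f is access, not use, and the 50%-use case is unlikely.

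**The timing is not fixed.** Section 5.2 says integration will begin, sites will be informed and recruitment will follow, without dates. The zero gap is assumed, the 4-month recruitment rests on an uncertain chart, and the 75% pairs that 4 months with a zero gap that no section states. This also stands, and is why a range is given.

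**The plan is not blind to the problem.** A reader might infer that nothing in 18.1 could tell dilution from a fading effect. The documents do not support that: group percentages at each survey and the discontinuation comparison in 1.1 would show a decline among intervention women. Healthcare utilization is also to be summarized. Whether those items record SexHealth Mobile visits cannot be known, because the survey tools are not in the documents. What remains open is the cause of a control rise.

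**The bias is conservative and spares the primary endpoint.** True; this limits the severity but does not correct the 3-month estimate.

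**Conclusion.** The concern holds as a minor one. The plan as written allows control women to use SexHealth Mobile before their 3-month survey, compares 3-month use by period without accounting for it, and could not attribute a control rise between 1 and 3 months. On the planning rates, with 50% access, the 3-month difference would be 53, 49 or 42 points instead of 56 at 10%, 25% or 50% use. This rests on uniform accrual, an assumed or apparent gap, users reaching 76%, and a use rate that the documents do not give.

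Two further inferences are not supported. A reader might conclude that contamination is expected; the documents show only that it is possible. A reader might also extend the point to the primary result or to power in the opioid use disorder subsample. The whole-sample 1-month test keeps power above 99.9% in the cases checked, and 18.2 claims subsample power only for the 1-month primary hypothesis, so no subsample claim is made for 3 months.

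**What to change.** 1. Reconcile 5.2 with the section 8 chart on when the service and its publicity open relative to control follow-up, and record the launch date at each site.
2. Check whether the healthcare-utilization items already identify use of any SexHealth Mobile service, whether on the mobile unit, on site or virtual. If not, make one item specific. Report the number of control users at each survey.
3. Treat that count as an approximate guide to direct use. It is tempting to read k users among n controls as a ceiling of k/n on the bias, but under-reporting and publicity that sends a woman elsewhere for contraception are not in k.
4. Add to 18.1 a supportive, descriptive 3-month comparison limited to control surveys dated before that site's launch, shown beside the full comparison.

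**Cost.** One date per site, at most one revised item, one reported count and one extra analysis; enrolment and the primary test do not change. The restricted comparison keeps about half of controls: 0.50 × 53 ≈ 27, range 13 (f = 75%) to 44 (f = 17%). It favors earlier enrollees and so carries some calendar-time selection. With 54 intervention women, the 95% half-width is 1.96 × √(0.20 × 0.80/27 + 0.76 × 0.24/54) = 0.189, about ±19 points. With all 53 controls it is ±16; with 13 it is about ±25. It should therefore be read together with the count of control users, not in place of the full comparison.
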